The names and contact information may be used to communicate with participants about other research studies related to workplace health promotion and chronic disease prevention (e.g. whether they would be interested in participating).

e. Consent. Will you obtain consent now from subjects for the banking and/or future sharing?

	No
	Yes

→ If yes, be sure to include the information about this consent process in the consent form (if there is one) and in your answers to the consent questions in [Section 8](#).

**f. Withdrawal.** Will subjects be able to withdraw their data/specimens from banking or sharing?

	No
	Yes

No

Yes → If yes, describe how, and whether there are any limitations on withdrawal.

*Example: data can be withdrawn from the repository but cannot be retrieved after they are released.*

If participants indicate that they do not want to have their information banked and shared, it will be removed from our records after this study has ended.

**g. Agreements for sharing or release.** Confirm by checking the box that you will comply with UW (and, if applicable, UW Medicine) policies that require a formal agreement between you and the recipient for release of data or specimens to individuals or entities other than federal databases.

	Confirmed
--	-----------

Confirmed

**5.11 Communication with subjects during the study.** Describe the types of communication (if any) you will have with already-enrolled subjects during the study. Provide a description instead of the actual materials themselves.

*Examples: email, texts, phone, or letter reminders about appointments or about returning study materials such as a questionnaire; requests to confirm contact information.*

Aim 1:

[redacted]

Aims 2/3:

Research team members will have multiple types of contact with the local health department staff, including emails, phone calls, and in-person meetings. Research team members' only direct contact with worksite representatives will be to collect their brief satisfaction survey data once, after the worksite has been doing Connect to Wellness for 12 months.

**5.12 Future contact with subjects.** Do you plan to retain any contact information you obtain for your subjects so that they can be contacted in the future?

	No
	Yes

No

Yes

→ If yes, describe the purpose of the future contact, and whether use of the contact information will be limited to your team; if not, describe who else could be provided with the contact information. Describe your criteria for approving requests for the information.

*Examples: inform subjects about other studies; ask subjects for additional information or medical record access that is not currently part of the study proposed in this application; obtain another sample.*

Aim 1:

[redacted]

Aims 2/3:

As mentioned above, participants' name and contact information will be retained. This information may be used to communicate with participants about other research studies related to workplace health promotion and chronic disease prevention.

**5.13 Alternatives to participation.** Are there any alternative procedures or treatments that might be advantageous to the subjects?

If there are no alternative procedures or treatments, select "No". Examples of advantageous alternatives: earning extra class credit in some time-equivalent way other than research participation; obtaining supportive care or a standard clinical treatment from a health care provider instead of participating in research with an experimental drug.

x	No
	Yes

→ If yes, describe the alternatives.

**5.14 Upload to the Supporting Documents** SmartForm of **Zipline** all data collection forms (if any) that will be directly used by or with the subjects, and any scripts/talking points you will use to collect the data. Do not include data collection forms that will be used to abstract data from other sources (such as medical or academic records, or video recordings).

- **Examples:** survey, questionnaires, subject logs or diaries, focus group questions.
- **NOTE:** Sometimes the IRB can approve the general content of surveys and other data collection instruments rather than the specific form itself. This prevents the need to submit a modification request for future minor changes that do not add new topics or increase the sensitivity of the questions. To request this general approval, use the text box below to identify the questionnaires/surveys/ etc. for which you are seeking this more general approval. Then briefly describe the scope of the topics you will cover and the most personal and sensitive questions. The HSD staff person who screens this application will let you know whether this is sufficient or whether you will need to provide more information.
- **For materials that cannot be uploaded:** upload screenshots or written descriptions that are sufficient to enable the IRB to understand the types of data that will be collected and the nature of the experience for the participant. You may also provide URLs (website addresses) or written descriptions below. Examples of materials that usually cannot be uploaded: mobile apps; computer-administered test; licensed and restricted standardized tests.
- **For data that will be gathered in an evolving way:** This refers to data collection/questions that are not pre-determined but rather are shaped during interactions with participants in response to observations and responses made during those interactions. If this applies to your research, provide a description of the process by which you will establish the data collection/questions as you interact with subjects, how you will document your data collection/questions, the topics you plan to address, the most sensitive type of information you will plan to gather, and the limitations (if any) on topics you will raise or pursue.

Use this text box (if desired) to provide:

- Short written descriptions of materials that cannot be uploaded, such as URLs
- A description of the process you will use for data that will be gathered in an evolving way.
- The general content of questionnaires, surveys and similar instruments for which you are seeking general approval. (See the **NOTE** bullet point in the instructions above.)

Aim 1:

[redacted]

**5.15 Send HSD a Confidentiality Agreement** if you will obtain or use any private identifiable UW records without subject's written consent (for example, screening medical records or class grades to identify possible subjects).

*The Confidentiality Agreement form must be completed, printed, signed, and mailed to the Human Subjects Division at [name]. Your IRB application cannot be approved until we receive the Confidentiality Agreement.*

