Aim 2 is a hybrid type III randomized controlled trial comparing two different *Connect to Wellness* implementation strategies. We will randomize 40 local health departments to receive either 1) standard training and technical assistance or 2) standard training plus enhanced technical assistance.

Aim 3 will measure the costs associated with each implementation strategy via process measures (e.g. tracking worksheets) and conduct a cost analysis based on this data.

**1.7 Intent.** Check all the descriptors that apply to your activity. You must place an “X” in at least one box.

*This question is essential for ensuring that your application is correctly reviewed. Please read each option carefully.*

Descriptor
 1. Class project or other activity whose purpose is to provide an educational experience for the researcher (for example, to learn about the process or methods of doing research).
 2. Part of an institution, organization, or program’s own internal operational monitoring.
 3. Improve the quality of service provided by a specific institution, organization, or program.
4. Designed to expand the knowledge base of a scientific discipline or other scholarly field of study, and produce results that: 

 • Are expected to be applicable to a larger population beyond the site of data collection or the specific subjects studied, or

 • Are intended to be used to develop, test, or support theories, principles, and statements of relationships, or to inform policy beyond the study.

 5. Focus directly on the specific individuals about whom the information or biospecimens are collected through oral history, journalism, biography, or historical scholarship activities, to provide an accurate and evidence-based portrayal of the individuals.
 6. A quality improvement or program improvement activity conducted to improve the implementation (delivery or quality) of an accepted practice, or to collect data about the implementation of the practice for clinical, practical, or administrative purposes. This does not include the evaluation of the efficacy of different accepted practices, or a comparison of their efficacy.

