## 5 PROCEDURES

**5.1 Study procedures.** Using lay language, provide a complete description of the study procedures, including the sequence, intervention or manipulation (if any), drug dosing information (if any), use of records, time required, and setting/location. If it is available and you think it would be helpful to the IRB: Upload a study flow sheet or table to the **Supporting Documents SmartForm** in **Zipline**.

*For studies comparing standards of care: It is important to accurately identify the research procedures. See UW IRB [POLICY: Risks of Harm from Standard Care](#) and the draft guidance from the federal Office of Human Research Protections, ["Guidance on Disclosing Reasonably Foreseeable Risks in Research Evaluating Standards of Care"](#), October 20, 2014.*

Aim 1:  
[redacted]

Aim 2:

Once a local health department has been recruited to participate in the study, they will be randomized to one of two conditions for the trial: 1) standard training and technical assistance or 2) standard training plus enhanced technical assistance.

Briefly, local health department staff will be trained to deliver the *Connect to Wellness* intervention to worksites that they recruit. In the Assessment phase, staff will measure current worksite implementation of physical activity, nutrition, cancer screening, and tobacco cessation evidence-based interventions (with the Baseline Employer Assessment Survey). [redacted] At the conclusion of the Implementation phase (month 12), the local health department staff will re-administer the Employer Assessment Survey. After this 12-month period, worksites are able to contact the local health department for technical assistance; the health department may also periodically contact worksites with study updates or to provide relevant materials or offer implementation support.

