Local health department staff will provide members of the research team with the contact information of worksite representatives from a sample of the worksites they recruit and deliver Connect to Wellness to. These representatives will be contacted via e-mail or telephone to schedule a time to complete the brief satisfaction survey. The survey will be administered by telephone.

Aim 3:

Following methods recommended by previous studies, we will assess the overall costs to implement the standard and enhanced training and technical assistance strategies, including all training and technical assistance activities conducted by the research team as well as activities performed by local health departments.

**5.2 Data variables.** Describe the specific data you will obtain (including a description of the most sensitive items). If you would prefer, you may upload a list of the data variables to the **Supporting Documents** SmartForm instead of describing the variables below.

Aim 1:

[redacted]

Aims 2/3:

We will collect the following data from local health department staff: 1) local health department characteristics; 2) satisfaction with training and technical assistance; 3) implementation and intent to maintain Connect to Wellness; and 5) staff and worksite activities, which will help us to determine which implementation strategy is more effective and the costs associated with each implementation strategy.

1. We will measure local health department characteristics using items from the 2016 National Profile of Local Health Departments. Sample measures include state, population size served, geographic region served, and governance (state, local, or shared). A co-investigator on this grant will pull these measures from the 2016 National Profile data, and we will ask staff to confirm their local health department's information.
2. We will ask staff to complete a brief online evaluation to assess satisfaction with and understanding of the training. We will also ask them to complete a satisfaction survey with the *Connect to Wellness* technical assistance they receive every six months and ask staff in the enhanced arm about their satisfaction with one-on-one support.

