Study Identification

Unique protocol identification number: STUDY00004627

Brief Title: Training LHD's to disseminate evidence-based interventions to small work sites

Official Title: Training Local Health Departments to Disseminate Evidence-Based Interventions to Small and Low-Wage Worksites

Secondary IDs: 2R01CA160217 [U.S. NIH Grant/Contract Award Number]
NCI-2021-02876 [Registry ID: CTRP (Clinical Trial Reporting Program)]
RG1121453 [Fred Hutch/University of Washington Cancer Consortium]

Document date: June 28th, 2017

This document includes the statistical analysis plan excerpted from our grant proposal. We completed this text on the above date.

Statistical analysis plan

To test whether LHDs in the enhanced arm recruit more worksites than LHDs in the standard arm, we will use a generalized linear model with log link. Robust standard error will be performed to obtain valid test results, since we expect the number of worksites recruited to be overdispersed relative to the Poisson distribution. We will perform a secondary analysis to test whether the rate of recruitment increases over time and whether such an increase is modified by treatment status. To study the time effects, we will analyze the number of worksite recruitments in 6-month intervals. The estimation will be implemented using a generalized estimating equation with an autoregressive working correlation matrix of order 1. Robust standard error will be performed to obtain valid test results of correlated outcome data. We will use linear models to study the worksite implementation score. Since worksites are nested within LHDs, we will implement the estimation using generalized estimating equation with robust standard error.

Power analysis. Our first primary outcome is the number of worksites recruited by each LHD during the study period (24 months). Based on power analysis using the Washington State pilot data, we propose a sample size of 40 LHDs (20 per arm) for this study. The mean number of worksites recruited over a 12-month period was 8.4 (sd=4.4). The proposed design will have at least 80% power to detect a mean difference of 2.6 worksites per year between the two arms. Our second primary outcome is the worksite implementation score, collected 12 months after the initial delivery of *Connect to Wellness*. Based on the preliminary results of the parent project, our design has at least 80% power to detect a 6% difference in implementation scores between the two intervention groups.

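### The primary model for worksites recruited has no baseline covariate, although population served is already obtained for each health department; prespecifying it could gain precision at almost no cost

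*Protocol*

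**What the plan says.** **Allocation.** Protocol 1.6 says "We will randomize 40 local health departments to receive either" one of two strategies. Section 5.1 (Aim 2) says that once an LHD is recruited, "they will be randomized to one of two conditions for the trial". No stratification, blocking, matching or sequence method is described, either as used or as not used. The SAP's power paragraph gives the split: "we propose a sample size of 40 LHDs (20 per arm) for this study".

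**Primary model.** To compare recruitment between arms, the SAP says "we will use a generalized linear model with log link", with robust standard errors because overdispersion is expected. It names no covariate, offset or stratum term. A secondary analysis looks at counts in 6-month intervals by generalized estimating equations (GEE), and again no baseline covariate is named.

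**Baseline data held.** Protocol 5.2, item 1, takes LHD characteristics from the 2016 National Profile and asks staff to confirm them: "Sample measures include state, population size served, geographic region served, and governance (state, local, or shared". These values exist before allocation. Neither document gives them a role in the arm comparison.

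**Power.** From the pilot, "The mean number of worksites recruited over a 12-month period was 8.4 (sd=4.4"). The claim is: "The proposed design will have at least 80% power to detect a mean difference of 2.6 worksites per year between the two arms".

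**The concern.** LHDs may come from any state or the District of Columbia, and each recruits small worksites in its own community. It is reasonable to expect that an LHD serving a larger population has more worksites to approach. If so, some of the large spread in the pilot counts (variance 19.36 against a mean of 8.4) reflects size, and the unadjusted model leaves that part in the error term.

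Two things are at stake. The first is power: there are only 20 units per arm, and the claimed 80% has little margin. The second is the estimate from the one allocation that actually occurs, because a chance difference in size between the arms would carry into an unadjusted comparison. Choosing the covariate in advance also avoids a choice made after the data are seen.

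**Working it through.** **Inputs.** From the SAP: 20 LHDs per arm, a difference of 2.6 per year, a 12-month mean of 8.4 and SD of 4.4, and 24 months of counting. Assumed, because the documents give neither: a two-sided 5% test, and the strength of the link between population and recruitment (r, or share of variance explained), shown as a range.

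**1. The plan's own power figure.** The 24-month SD is not stated, so I express it per year under three assumptions:
- Independent years: 4.4/√2 = 3.11.
- Persistent LHD effect plus Poisson noise: extra-Poisson variance 19.36 − 8.4 = 10.96; 24-month variance 2 × 8.4 + 4 × 10.96 = 60.64; SD 7.79, or 3.89 per year.
- Perfectly correlated years: 4.4.

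The standard error of the arm difference is SD × √(2/20), which gives 0.98, 1.23 and 1.39. Normal-approximation power, Φ(2.6/SE − 1.96), is 75%, 56% and 46%. The t-test gives 73%, 54% and 45%. The stated 80% appears only under choices that the SAP does not state, for example Poisson variance over 12 months (SE = √8.4 × 0.316 = 0.917, power 81%), or a one-sided test with independent years (84%). The figure is therefore not reproduced from its stated inputs, but it is not shown to be wrong.

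**2. Room for a covariate.** 10.96/19.36 = 57% of the 12-month pilot variance is beyond Poisson. This is a rough ceiling for all stable LHD traits together. It is not an estimate for population size.

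**3. Linear approximation with adjustment.** Residual SD = SD × √(1 − r²); two-sample t-test at 2.6 per year:

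| SD per year | r = 0 | 0.1 | 0.3 | 0.5 | 0.6 |
|---|---|---|---|---|---|
| 3.11 (independent years) | 73% | 73% | 77% | 85% | 90% |
| 3.89 (persistent effect) | 54% | 54% | 58% | 66% | 73% |
| 4.4 (perfectly correlated) | 45% | 45% | 48% | 56% | 62% |

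The first row does not fit the concern well: a fixed LHD trait that predicts recruitment makes an LHD's years correlated. The second row is the more coherent case.

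**4. Simulation of the SAP's model.** Log link, robust standard error, 40 LHDs, 24-month counts, persistent LHD effects, 8.4 v 8.4 + 2.6 = 11.0 per year:

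| Share of between-LHD log-rate variance explained by population | Unadjusted | Adjusted |
|---|---|---|
| 0% | about 51% | about 51% |
| 10% | about 51% | about 54% |
| 25% | about 51% | about 60% |
| 50% | about 51% | about 68% |

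A second simulation of the same model gave about 46% unadjusted and 46%, 48%, 52% and 63% adjusted. The level depends on details such as the small-sample handling of the robust standard error. The pattern does not: no gain at 0%, a few points at 10%, and about 17 points at 50%. Unadjusted type I error under simple allocation was 5 to 6%, and adjustment did not change it materially.

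**5. Chance imbalance.** If allocation is simple 20:20, the standardised difference in a baseline variable has SD √(2/20) = 0.316. Then P(|difference| > 0.3) = 2(1 − Φ(0.3/0.316)) = 34%, and for 0.5 it is 11%. At r = 0.5, an imbalance of 0.3 SD moves the arm difference by 0.5 × 0.3 × SD, which is 0.47, 0.58 or 0.66 per year for the three SDs. That is 18 to 25% of 2.6, but only about 0.47 of a standard error in each case (0.47/0.98; 0.66/1.39).

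**The case against.** The strongest reply is that nothing in the documents shows that population predicts recruitment. Protocol 2.2 asks every LHD, whatever its size, to be willing to recruit at least 15 worksites in 24 months. That is 7.5 a year, close to the pilot mean of 8.4. Section 4.1 screens out LHDs that cannot commit staff and time. Staff capacity may therefore be the limit, and with r near zero adjustment gains nothing. This stands, and it is why the gain is given as a range that starts at none. It does not remove the case for adjusting, because the loss is then also close to nil (about 51% either way).

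Three stronger readings are tempting, and the documents support none of them:
- *The trial randomises without stratification.* The protocol text is a lay-language ethics application and the SAP is an excerpt from a grant proposal. They are silent on the method, and silence does not establish simple allocation. The 34% figure is conditional on it.
- *Imbalance makes the primary test invalid.* It does not. Randomisation keeps the unconditional type I error near nominal, and the unadjusted standard error already allows for shifts of this size. What remains is lost precision and conditional bias in the one realised allocation.
- *Adjustment lifts power from 73% to 85%.* That needs r = 0.5 and independent years together. Neither is in the documents, and the two fit poorly with each other.

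**Conclusion.** The point holds as a matter of precision. The stated primary model ignores a baseline value that the trial obtains for each LHD and that is a plausible, undemonstrated predictor of the outcome. The unadjusted test is valid. The possible gain in power runs from nothing, if population is unrelated to recruitment, to about 17 percentage points if it explains half of the between-LHD log-rate variance; at 10 to 25% it is about 2 to 9 points. These figures assume a two-sided 5% test, persistent LHD effects and the pilot mean and SD. The point concerns the first primary outcome and its 6-month analysis, and does not extend to the worksite implementation score. The firm part is the covariate, because the SAP does state its model. The allocation part rests on silence and is secondary.

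**What to change.** Add to the SAP: *The primary log-link model, and the 6-month-interval GEE, include log population served (2016 National Profile) as a prespecified covariate; the unadjusted result is reported as a sensitivity analysis.*

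Use it as a covariate and not as an offset. An offset would force recruitment to be proportional to population, which sits poorly with a common expectation of 15 worksites.

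Stratified allocation is optional. If it is used, fix the size cut-point in advance, since the sample median is unknown while LHDs are still enrolling, and keep the size term in the model. In simulation, two-stratum allocation without the term made the test conservative (type I error 3.5% when population explained 50% of the between-LHD variance) and brought no power gain. Blocks tied to the five-LHD training groups within size strata are best avoided, because they could make those peer groups all small or all large.

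Cost: one degree of freedom and one sentence, with no new data. The downside is little or no gain if population turns out not to be prognostic. In the same revision, state the alpha, the sidedness and the 24-month SD behind the power claim so that it can be reproduced.

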Once a local health department is assigned to the standard arm, a member of the research team will contact staff to arrange dates for the training sessions, ship materials for the worksites (e.g. toolkits), and provide a detailed *Connect to Wellness* protocol to use with worksites that they recruit. The research team will e-mail information about the *Connect to Wellness* training website and ensure that staff are able to register. Local health department staff will attend three online training webinars, each lasting two hours, in groups of five. (Note: Five refers to the number of local health departments represented in each group). These real-time webinars will be supported by Zoom software. Topics covered in this training will include an introduction to *Connect to Wellness*, methods for recruiting worksites, how to administer the Employer Assessment Survey, how to create and deliver the recommendations report, an overview of intervention implementation and programming, how to track (e.g. their interactions with worksites, time spent on project), and discussion of common barriers and solutions. At the conclusion of the third training webinar, we will work with each group of local health departments to identify a time for monthly group technical assistance calls, where staff will have time to share lessons learned and success stories. Features will be added to the *Connect to Wellness* website to encourage communication between members of each five-local health department group, such as discussion forums and instant chat.

Local health departments assigned to the enhanced arm will undergo initial and online training procedures as described above. Each group will also have a monthly technical assistance call and access to the online peer-communication tools described above. In addition, local health departments in this arm will have one-on-one telephone access to a member of our research team. They can call her for advice; she will proactively contact each local health department in this arm monthly if they have not contacted her during that time. Enhanced support will be given for 24 months, the same length as the study period for this aim.

Throughout the study period, members of the research team will contact local health department staff via e-mail or telephone to obtain study data (measures described in Section 5.2). REDCap will be primarily used for data collection.

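### Both arms get training and technical assistance in groups of five LHDs, but neither primary analysis nor the power statement allows for correlation within those groups

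*Protocol*

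**What the plan says.** Allocation is by LHD. Protocol section 5.1 (Aim 2) states: "Once a local health department has been recruited to participate in the study, they will be randomized to one of two conditions for the trial". The SAP's power paragraph sets the number: "we propose a sample size of 40 LHDs (20 per arm) for this study".

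Delivery is by group. Section 5.1 says "Local health department staff will attend three online training webinars, each lasting two hours, in groups of five" and clarifies that "Five refers to the number of local health departments represented in each group". After the third webinar, "we will work with each group of local health departments to identify a time for monthly group technical assistance calls", so that staff can exchange experience. Website features are added to "encourage communication between members of each five-local health department group, such as discussion forums and instant chat". The enhanced arm has the same format plus one-on-one support: "Each group will also have a monthly technical assistance call and access to the online peer-communication tools described above". Both copies of the protocol form in the file describe this in the same way.

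The SAP tests the number of worksites recruited with a log-link generalized linear model. Its robust standard error is justified only by overdispersion relative to the Poisson. For the implementation score it says: "Since worksites are nested within LHDs, we will implement the estimation using generalized estimating equation with robust standard error". The training group appears in neither model and not in the power text.

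**The concern.** LHDs are randomised one by one, but after assignment they are taught together and encouraged to learn from each other. The webinars cover how to recruit worksites and how to administer the Employer Assessment Survey, so what the group shares bears directly on both primary outcomes. A lively group may lift all five of its LHDs; a passive one may not.

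A robust standard error at LHD level protects against a misspecified variance for each LHD, but it still assumes that LHDs are independent of each other. It does not see covariance between LHDs in the same group. Where that covariance is positive and groups sit within arms, variation between groups is partly read as a difference between arms. Both primary confidence intervals are then too narrow, and the false-positive rate exceeds its nominal value. The SAP already accepts this reasoning one level down, for worksites within LHDs.

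**Working it through.** **Inputs from the documents.** 40 LHDs, 20 per arm; groups of 5; pilot mean 8.4 worksites per 12 months, SD 4.4; target difference 2.6 per year; stated power at least 80% (SAP, power paragraph).

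**Assumptions.** Two-sided 5% level (the SAP states none). Groups formed within arm, so 20/5 = 4 groups per arm, 8 in all. ICC between LHDs in the same group from 0 to 0.20.

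**1. The plan's own power figure.**
- Overdispersion: φ = 4.4²/8.4 = 2.305.
- Log-link Wald calculation over 24 months with 8.4 per year as the higher arm (8.4 vs 5.8): log ratio = ln(8.4/5.8) = 0.370; SE = sqrt[(2.305/20)×(1/16.8 + 1/11.6)] = 0.1296; ratio 2.858; power 81.5%.
- With 8.4 as the lower arm (8.4 vs 11.0), the same formula gives 69%.
- A plain comparison of means gives 46% on 12-month figures (2.6, SD 4.4), and 75% on 24-month figures (5.2, SD 4.4×√2 = 6.22).

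So the 80% is matched by the 81.5% variant, which rests on unstated choices and has no group term. The power claim for the score (a 6% difference) cannot be reproduced, because no SD, ICC or number of worksites enters it.

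**2. Standard error for the count.** The variance of an arm mean is multiplied by 1+(5−1)×ICC, so the true SE divided by the LHD-level SE is sqrt(1+4×ICC).

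**3. Type I error for the count.** The analytic value is 2×P(t38 > 2.024/sqrt(1+4×ICC)). The simulations use 8 groups of 5, a 24-month mean of 16.8, overdispersion from the pilot SD, and the robust log-link test with a t reference on 38 df.

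| Assumed ICC | SE ratio | Analytic | Simulated |
|---|---|---|---|
| 0 | 1.00 | 5.0% | about 5.5% |
| 0.02 | 1.04 | 5.9% | 6–7% |
| 0.05 | 1.10 | 7.2% | about 8% |
| 0.10 | 1.18 | 9.5% | 10–11% |
| 0.20 | 1.34 | 14.0% | 16% |

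The excess at ICC 0 is small-sample bias in the robust SE, not grouping; only the rise above that row is due to groups. With a normal reference instead of t, the simulated values are higher (6.4% at ICC 0, 12% at 0.10). A test on group means with 8−2 = 6 df held about 5% throughout.

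**4. Implementation score.** Assume 15 worksites per LHD (the recruitment commitment in protocol section 2.2) and a total LHD-level ICC of 0.10. A group component of 0.01 then gives a correlation between LHD means of 0.01/(0.10 + 0.90/15) = 0.0625; a component of 0.02 gives 0.125. Simulated type I error with clustering on LHD only and a normal reference is 6.3% with no group component, 9.9% at 0.01 and 13.4% at 0.02. A small worksite-level group ICC is therefore not automatically harmless here.

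**5. Power when group is accounted for.** Starting from the 81.5% variant, divide 2.858 by sqrt(1+4×ICC).

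| Assumed ICC | Normal reference | t on 6 df |
|---|---|---|
| 0 | 81.5% | 67% |
| 0.05 | 74% | 59% |
| 0.10 | 68% | 53% |
| 0.20 | 57% | 43% |

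**The case against.** The strongest reply is that the harm is conditional. A reader might infer that both primary standard errors are certainly too small. The documents do not support that: they give no within-group correlation. At ICC 0 grouping does no harm, and at 0.01 the SE for the count is only about 2% low. All groups share one curriculum, website and delivery protocol, and nothing says that different groups have different facilitators. This stands, and the point is worded as conditional for that reason.

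A reader might also infer that membership is fixed for two years. The 24 months is stated for the enhanced support and for the study period; no sentence says how long group calls run or that groups never change. Likewise, four groups per arm is an inference. It is the natural reading, since grouping follows assignment and the enhanced arm's groups are described separately, but no sentence says so. If groups mixed the arms, group effects would partly cancel in the comparison and the direction of the error could differ. These gaps are reasons for the SAP to say how groups are formed; they do not justify leaving the level out.

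Individual randomisation is not a defence, because the correlation would arise after assignment.

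Finally, the remedy has a price. A test on 6 df misses 80% power even if groups do not matter, and the exact method with so few groups is a judgement. Both are true. They argue for stating the choice and its cost in advance.

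**Conclusion.** The omission is a matter of record: delivery is in groups of five in both arms, and neither primary analysis nor the power statement carries that level. The consequence is conditional. If outcomes correlate positively within groups and groups are formed within arm, the LHD-level SE for the count is too small by sqrt(1+4×ICC), and robust standard errors as specified do not repair it. Type I error then ranges from a negligible excess at ICC 0.02 or less to about two to three times nominal at 0.10 to 0.20. All ICC values are assumptions, as are the two-sided 5% level and, for the score, the 15 worksites per LHD and the total LHD ICC of 0.10. The size is unknown and could be small. Positive correlation is nevertheless what the peer features are meant to bring about, and the choice of variance level could change the conclusion on either primary outcome.

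**What to change.** In the protocol or SAP, state how the groups of five are formed: within arm or not, and whether membership is stable. Carry the group ID in the analysis dataset; the team already tracks each LHD's attendance at training and group calls (protocol section 5.2).

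In the SAP, account for group in both primary analyses. Either cluster the variance on group, or fit a mixed model with random intercepts for group and LHD. Use a small-sample correction with about 6 df if there are 8 groups within arms. Settle this before outcome data are seen.

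Restate power over a range of ICCs, giving the level, sidedness, time scaling and which arm has mean 8.4.

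Cost: SAP wording and one variable; no extra LHDs or data are needed for a valid test. The downside is wider intervals and lower stated power, as the last table shows. If the sponsor wished to hold nominal power, the design effect alone (40×(1+4×ICC)) would call for 48 LHDs at ICC 0.05 and 56 at 0.10, before any loss from the 6 df.
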